## **8.2 Carriage cohort**

### **Maternal carriage**

Maternal bacterial carriage will be analysed by estimating the proportion of women positive at day 6 and the proportion positive at one or more of the post-intervention time points (i.e. day 6, day 28 or 4 months). The latter will be estimated using women who have data available at all time points, i.e. women missing day 28 or 4-month data will be excluded from this analysis. However, a secondary analysis will be done using a multiply imputed dataset in which missing day 28 and 4-month carriage data are imputed using day 0 and day 6 data. For bacteria that are isolated from multiple sample types an individual will be identified as positive if bacteria are isolated from any of the samples (Table 5). For example,

women will be considered positive for *Klebsiella* at day 6 if bacteria are isolated from either the NPS or breast milk sample. Besides presenting the prevalence of individual bacteria, the bacteria will be grouped into gram positives (*S. pneumoniae*, *S. aureus*, GBS, GAS) and gram negatives (*E. coli*, *pseudomonas*, *Klebsiella*).

We will use logistic regression to compare the proportion positive by study arm adjusting for carriage at day 0. For example, *S. aureus* carriage on day 6 will be compared by calculating an odds ratio adjusted for *S. aureus* carriage on day 0. If the prevalence of a carriage outcome is <4% then an unadjusted odds ratio will be presented instead of the adjusted OR and Fisher's exact test will be used to calculate the p-value. The cut-off of 4% has been chosen to ensure that logistic regression is not used when there are fewer than 10 events per parameter as recommended by Peduzzi et al (1996).

A longitudinal analysis of carriage will be conducted using data from breast milk samples collected on day 6, day 28 and at 4 months. As with the other analyses, logistic regression will be used to adjust for carriage at day 0 where possible (i.e. provided the prevalence is  $\geq 4\%$ ). Two versions of the analysis will be done: the first will be restricted to women with complete data at all three time points, and the second will be done using the multiply imputed dataset. The prevalence at each time point and in each arm will be displayed graphically.

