## 4 Study Methods

### 4.1 General Study Design and Plan

(ICH E3; 9)

PregnAnZI-2 was a phase III, double-blinded, placebo-controlled randomized clinical trial in which women in labour were randomized to either a single 2g dose of oral AZI or placebo. The study recruited 12,000 women (6750 in The Gambia and 5250 in Burkina Faso).

In The Gambia, women were recruited in two health facilities—Bundung Maternal and Child Health Hospital and Serrekunda Health Centre. In Burkina Faso, recruitment took place in a number of health facilities in Nanoro and Yako health districts.

Women were consented during the antenatal care visits but the study number (randomisation number) was only assigned after screening during labour, provided the woman met the necessary inclusion and exclusion criteria for participation.

Before March 23rd 2020, women and their newborns were visited at 28 day (either at home or at the health facility). After March 23rd 2020, women were not visited at home because of the risk of SARS-CoV-2 transmission, instead the day 28 interview was conducted by telephone. Cases of maternal and neonatal sepsis were identified through passive case detection at the study health facilities during the 28-day follow up period.

Additional scheduled visits at 6 and 12 months were performed for the first 2,000 women recruited (half in The Gambia and half in Burkina Faso) to assess infant anthropometrical measurements, hospitalization and all-cause mortality.

Carriage samples (recto-vaginal swabs, NPS, OPS, rectal swabs and breast milk samples) were collected from 500 randomly selected mother-newborn dyads (or triads in the case of twins). The samples were collected at day 0, day 6, day 28 and at 4 months.

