#### Carriage cohort

The cohort will include all mother–newborn dyads/triads who meet the following criteria:

- Selected to be in the carriage cohort
- Included in the primary analysis cohort
- Contributed swabs at day 0 and day 6 (but not necessarily at day 28 or 4 months)
- All members of the dyad/triad alive and participating in the study at the time of the 4–month visit

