### Carriage and Anthropometric cohorts

Since outcomes are actively recorded in these cohorts, missing data may be recorded for some of the outcomes analysed in the Carriage and Anthropometric cohorts.

We anticipate some missing data at the 4-month time point because of the interruption due to the COVID-19 pandemic. Therefore, an available case analysis will be conducted in the Carriage cohort. The occurrence of missing data is unlikely to be associated with any particular characteristic of the women/neonates, and the risk of bias due to missing data is small.

The anthropometric cohort was recruited prior to the COVID-19 pandemic. Nevertheless, we expect some missing data due to loss to follow up, and will therefore conduct an available case analysis in this cohort. We will assess the risk of selection bias by comparing the baseline characteristics of children who are lost to follow up with those who remain in the cohort throughout follow up.

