### **Infant carriage**

With the exception of *Klebsiella*, which is tested for in NPS and RS, in samples collected from infants each bacteria is only tested for in one sample type (e.g. *S. pneumoniae* is tested for in NPS and *E.coli* is tested for in rectal swabs). Therefore, in contrast to the analysis of maternal carriage, there is no need to combine results across different sample types. Each bacteria will be compared between study arms at day 0, day 6, day 28 and 4 months (Table 4). Additionally, we will compare the proportion positive at any time point. We will use logistic regression to adjust for maternal carriage at day 0 if the prevalence is  $\geq 4\%$ , if the prevalence is less than this then we will calculate an unadjusted OR and use Fisher's exact test. Note that we have chosen to adjust for maternal carriage at day 0 rather than neonatal carriage because neonatal samples are collected after treatment and may, therefore, be affected by treatment. The prevalence at each time point and in each arm will be displayed graphically. As with the analysis of maternal carriage, the analyses will be

done in children with complete data and then repeated using multiply imputed data (missing day 28 and 4-month outcomes will be imputed from day 0 and day 6 outcomes).

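### The stated imputation model for late carriage does not list study arm, so the imputed arm comparisons can be biased, in a direction that depends on how the effect evolves

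*SAP*

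**What the plan says.** In SAP section 8.2, under Maternal carriage, the main estimate of being positive at any post-treatment visit uses women with complete data, and "a secondary analysis will be done using a multiply imputed dataset". The rule given there for filling the gaps is that "missing day 28 and 4-month carriage data are imputed using day 0 and day 6 data". The longitudinal breast-milk analysis is also run in both versions. Under Infant carriage the analyses are "done in children with complete data and then repeated using multiply imputed data". The corresponding rule for infants reads: "missing day 28 and 4-month outcomes will be imputed from day 0 and day 6 outcomes". Section 8.2 also says that resistance will be analysed in the same way as overall carriage, so the rule extends to it.

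The model then fitted is an arm comparison: "We will use logistic regression to compare the proportion positive by study arm adjusting for carriage at day 0". For infants the adjustment is for maternal day-0 carriage.

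Section 6.2 confines the missing values to the late visits, because a dyad enters the cohort only if it "Contributed swabs at day 0 and day 6 (but not necessarily at day 28 or 4 months)". Section 6.4 says: "We anticipate some missing data at the 4-month time point because of the interruption due to the COVID-19 pandemic". It gives no expected fraction, and it regards missingness as unlikely to depend on participant characteristics. No section names study arm as an imputation predictor or says that imputation is done within arm. No section says that arm is excluded.

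**The concern.** An imputation model should contain the variables of the analysis model, above all the one whose coefficient is reported. Here that variable is study arm. With day-0 and day-6 results as the only predictors, a missing late value is drawn from the same distribution in both arms for participants with the same earlier carriage. The imputed records therefore contain only the part of the late arm difference that day-6 carriage explains.

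The imputed analysis is the only alternative to complete data that section 8.2 describes for these outcomes. If missingness is unrelated to participants, as section 6.4 expects, the complete-data comparison is not biased by it. The imputation would then add a bias of its own, and a gap between the two versions could be misread as evidence that missing data matter. For resistance, a persisting increase under azithromycin could be understated.

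**Working it through.** The SAP states no figure on this point, so there is nothing to reproduce. The carriage rates and missing fractions below are assumptions.

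**Inputs from the SAP.** Cohort size: samples "were collected from 500 randomly selected mother-newborn dyads" (section 4.1), taken as 250 per arm. Day-0 and day-6 results are complete (section 6.2). Missingness is unrelated to participants (section 6.4). Predictors and analysis model are those of section 8.2.

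**Assumed.** Missing fraction m = 10%, 20%, 40%. Within each arm, the odds ratio linking day-6 and late carriage is 3 unless stated.

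**Large-sample calculation** (day 0 left out for simplicity). Let s be day-6 carriage in an arm, y late carriage, and x the proportion positive at both, fixed by the within-arm odds ratio. With equal arms:

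- Pooled P(late | day 6 positive) = (sum of x) / (sum of s) = A
- Pooled P(late | day 6 negative) = (sum of y − sum of x) / (2 − sum of s) = B
- Imputed late rate in an arm = s·A + (1 − s)·B
- Analysed rate = (1 − m)·y + m·(imputed rate)

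*Effect persists: day 6 and late both 30% placebo, 15% azithromycin.*
- x = 0.1407 and 0.0447.
- A = 0.1854/0.45 = 0.412; B = (0.45 − 0.1854)/1.55 = 0.1707.
- Imputed rates: 0.3 × 0.412 + 0.7 × 0.1707 = 0.243 (placebo); 0.15 × 0.412 + 0.85 × 0.1707 = 0.207 (azithromycin). The 15-point difference shrinks to 3.6 points in the imputed records.
- At m = 40%: 0.6 × 0.30 + 0.4 × 0.243 = 0.277 and 0.6 × 0.15 + 0.4 × 0.207 = 0.173, giving an odds ratio of 0.54 against a true 0.41.

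*Early suppression, full recovery: day 6 30% and 15%, late 30% in both arms.*
- x = 0.1407 and 0.0774; A = 0.485, B = 0.246.
- Imputed rates 0.318 and 0.282: a difference appears where there is none.
- At m = 40%: 0.307 and 0.293, odds ratio 0.93 against a true 1.00.

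*Carriage raised by treatment, as resistance could be: day 6 5% and 15%, late 5% and 12%.* Same formulas.

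| Scenario | True OR | 10% missing | 20% | 40% |
|---|---|---|---|---|
| Effect persists | 0.41 | 0.44 | 0.47 | 0.54 |
| Recovery | 1.00 | 0.98 | 0.97 | 0.93 |
| Recovery, day 6-to-late OR 8 | 1.00 | 0.97 | 0.94 | 0.88 |
| Raised by treatment | 2.59 | 2.38 | 2.20 | 1.88 |
| Effect persists, positive at day 6 or late | 0.40 | 0.42 | 0.43 | 0.47 |

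The any-time outcome moves less because its day-6 part is always observed.

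**Simulation at the trial's size.** n = 500, 400 replicates, 10 imputations with parameter draws. The analysis model is arm plus day 0; the imputation model is day 0 plus day 6, without or with arm. Day-0 carriage is 30%. The logit of day-6 carriage is −1.2 + 1.2·day0 − 1.0·arm; the logit of late carriage is −1.3 + 0.6·day0 + 1.1·day6 + b·arm. Mean log odds ratios for arm:

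| Direct late effect b | Missing | Full data | Imputed, no arm | Imputed, with arm |
|---|---|---|---|---|
| −0.7 | 10% | −0.90 | −0.83 | −0.90 |
| −0.7 | 20% | −0.88 | −0.74 | −0.87 |
| −0.7 | 40% | −0.90 | −0.62 | −0.90 |
| 0 | 40% | −0.197 | −0.193 | −0.191 |

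With a direct late effect, leaving arm out shrinks the log odds ratio by 31% at 40% missing ((0.902 − 0.620)/0.902) and by 8% at 10% missing ((0.896 − 0.826)/0.896). Including arm removes this bias. With no direct effect, leaving arm out does no material harm.

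**The case against.** The strongest reply is that the SAP is silent on arm rather than excluding it. Its wording may only say which visits inform the missing ones, and for mothers it speaks of data, which is broader than carriage. That stands as far as intention goes: arm may always have been meant. But the infant text names outcomes, and study arm is not one. Elsewhere the SAP names its model covariates, so a programmer would fairly take the list as the specification.

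A reader might also infer that the imputed analyses are always pulled towards no effect, and so would wrongly suggest that effects fade by 4 months. The documents do not support that. The intervention is a single dose and the last sample is at 4 months, so recovery of carriage is plausible. In that case the rule carries the early difference forward and biases away from 1.

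Reach is limited too: the imputed analysis is secondary for mothers and a repeat for infants. With little missing data the shift is small. Finally, sparse organisms limit how many predictors can be added. The SAP's 4% cut-off gives 0.04 × 500 = 20 events, or 10 for each of two parameters. That is a fair argument for a short predictor list, but not for leaving out the variable being tested.

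**Conclusion.** The point holds as a fault in a stated rule for secondary analyses. As written, the imputation omits the comparison variable. The imputed odds ratios can then be biased towards 1 when a direct late effect in the same direction persists, away from 1 when early suppression is followed by recovery, and hardly at all when the effect runs wholly through day-6 carriage. Because the pattern is unknown in advance, the imputed version is not a dependable check on the complete-data one.

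The sizes above rest on assumed carriage rates, an assumed day 6-to-late association, missingness unrelated to participants, and missing fractions that the SAP does not give. None is a forecast for this trial. The results affected are the imputed versions of infant day-28, 4-month and any-time carriage, maternal any-time carriage, the longitudinal breast-milk analysis, and the matching resistance analyses. The primary endpoint, day-6 comparisons and all complete-data carriage results are unaffected.

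**What to change.** In section 8.2, under both Maternal carriage and Infant carriage, state that the imputation model for each organism includes study arm together with day-0 and day-6 carriage, or that imputation is done separately by arm. Say that the same applies to resistance. Where the data are not too sparse, add any observed day-28 or 4-month result for the same organism; if predictors must be dropped, keep arm. Country need not be added, since section 6.6 leaves it out of the carriage analysis because of the cohort's size.

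The cost is a sentence in each place and one more variable (or a by-arm option) in the imputation code. No new data are needed. If arm was always intended, the sentence simply records it.

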#### Carriage cohort (500 mothers and their children –250 pairs per country)

1. *S. pneumoniae* in infant nasopharyngeal swabs
2. *Klebsiella* in infant nasopharyngeal swabs
3. *E. coli* in infant rectal swabs
4. *Klebsiella* in infant rectal swabs
5. *Pseudomonas* in infant rectal swabs
6. *S. aureus* in infant oropharyngeal swabs

7. GBS in infant oropharyngeal swabs
8. GAS in infant oropharyngeal swabs
9. *S. aureus* in breast milk samples
10. GBS in breast milk samples
11. GAS in breast milk samples
12. *E. coli* in breast milk samples
13. *Pseudomonas* in breast milk samples
14. *Klebsiella* in breast milk samples
15. *E. coli* in NPS collected from women
16. *S. pneumoniae* in NPS collected from women
17. *Klebsiella* in NPS collected from women
18. *S. aureus* in OPS collected from women
19. GBS in OPS collected from women
20. GAS in OPS collected from women
21. Resistance to AZI, oxacillin and amoxicillin among isolates of *S. aureus*
22. Resistance to AZI, oxacillin and amoxicillin among isolates of GBS
23. Resistance to AZI, oxacillin and amoxicillin among isolates of GAS
24. Resistance to AZI, oxacillin and amoxicillin among isolates of *S. pneumoniae*
25. Resistance to AZI, oxacillin and amoxicillin among isolates of *Klebsiella*

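### Five of the six maternal nasopharyngeal and oropharyngeal carriage endpoints in SAP section 3.4 have no analysis as listed, because section 8.2 pools swabs with breast milk

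*SAP*

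**What the plan says.** SAP section 3.4, under the carriage cohort, numbers the maternal endpoints by specimen. Items 9 to 14 are six bacteria in breast milk. Items 15 to 17 are E. coli, S. pneumoniae and Klebsiella in NPS. Items 18 to 20 are S. aureus, GBS and GAS in OPS, worded for example as "GBS in OPS collected from women" and "GAS in OPS collected from women".

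Table 5 in section 4.4 gives the maternal sampling. NPS and OPS are taken on day 0 before treatment and on day 6, breast milk on day 6, day 28 and at 4 months, and the recto-vaginal swab on day 0 only.

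Section 8.2, under maternal carriage, sets the outcomes as positive at day 6 and positive at one or more post-intervention time points. For a bacterium sought in more than one sample type, "an individual will be identified as positive if bacteria are isolated from any of the samples (Table 5"). Its worked example is Klebsiella at day 6, counted from either the NPS or the milk. A separate longitudinal analysis is then specified, using breast milk alone.

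**The concern.** The listed endpoints and the specified analysis do not match. A reader of section 3.4 expects a between-arm comparison of, say, GBS in the throat. Section 8.2 supplies a comparison of GBS in throat or milk, and a separate one of GBS in milk, but none of GBS in the throat.

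At stake is whether the trial reports on the endpoints it names. A pooled result showing no difference could hide a change in throat or nasopharyngeal carriage. A pooled difference could come wholly from milk and be read as an effect on maternal carriage in general. Either way the site is lost, although each site is sampled and cultured separately.

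**Working it through.** **1. Which listed endpoints are pooled.** Setting section 3.4 beside Table 5 and section 8.2:

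| Item in 3.4 | Listed endpoint | Bacterium also sought in milk? | Day-6 outcome under 8.2 | Analysed as listed? |
|---|---|---|---|---|
| 15 | E. coli, NPS | Yes | NPS or milk | No |
| 16 | S. pneumoniae, NPS | No | NPS | Yes |
| 17 | Klebsiella, NPS | Yes | NPS or milk | No |
| 18 | S. aureus, OPS | Yes | OPS or milk | No |
| 19 | GBS, OPS | Yes | OPS or milk | No |
| 20 | GAS, OPS | Yes | OPS or milk | No |

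Five of six have no analysis as listed. Day 6 is the only post-treatment swab for mothers, so the second outcome in 8.2 (positive at any post-intervention time point) cannot fill the gap: it adds further milk samples to the same composite. The general rule for secondary outcomes in section 8.1 belongs to the primary analysis cohort and does not fill it either.

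**2. The one figure in this part of 8.2.** The 4% prevalence cut-off is meant to secure 10 events per parameter. With 500 women, 500 × 0.04 = 20 events; with two parameters (arm and day-0 carriage), 20 / 2 = 10. It reproduces, and it can serve unchanged for specimen-specific comparisons.

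**3. What pooling does to the effect.** The SAP gives no carriage prevalence, effect size or correlation between sites, so every prevalence below is an assumption. Take 250 women per arm (equal split of 500, also assumed) and two-sided 5%.

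- Independent sites: pooled prevalence = 1 − (1 − swab)(1 − milk).
- Milk positives all among swab positives (nested): pooled prevalence = swab prevalence.
- Odds ratio (OR), azithromycin v placebo = [p_A/(1 − p_A)] / [p_P/(1 − p_P)].
- Power: normal approximation for two proportions, with pooled variance under the null and separate variances under the alternative.

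Swab alone, 30% placebo v 18% azithromycin: OR = (0.18/0.82)/(0.30/0.70) = 0.51, power 0.88.

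| Assumed milk carriage, placebo / azithromycin | Relation to swab | Pooled, placebo / azithromycin | OR | Power |
|---|---|---|---|---|
| 5% / 5% | independent | 33.5% / 22.1% | 0.56 | 0.81 |
| 15% / 15% | independent | 40.5% / 30.3% | 0.64 | 0.67 |
| 30% / 30% | independent | 51.0% / 42.6% | 0.71 | 0.47 |
| 15% / 15% | nested in swab | 30.0% / 18.0% | 0.51 | 0.88 |
| 15% / 9% | independent | 40.5% / 25.4% | 0.50 | 0.95 |
| 15% / 5% | independent | 40.5% / 22.1% | 0.42 | 0.99 |

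Example, second row: 1 − 0.70 × 0.85 = 0.405 and 1 − 0.82 × 0.85 = 0.303; OR = (0.303/0.697)/(0.405/0.595) = 0.64.

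**4. A pooled effect with none at the swab site.** Let swab carriage be 10% in both arms and milk 20% v 10%, independent. Pooled: 1 − 0.90 × 0.80 = 0.28 and 1 − 0.90 × 0.90 = 0.19; OR = (0.19/0.81)/(0.28/0.72) = 0.60, although the swab OR is 1.

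**The case against.** The strongest reply is that pooling is deliberate and disclosed. Section 8.2 states the rule with an example, and its infant part explains that no such combining is needed there. Carriage at any maternal site is a legitimate prespecified quantity, and the milk endpoints keep their own analysis. Only five of the 25 carriage items are touched, all secondary in a 500-pair substudy. All of this stands, and it is why the pooled analysis need not be removed or demoted. It does not supply the missing analyses.

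Three stronger readings are tempting, and the SAP does not support them.

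- *That pooling dilutes the effects.* This follows only if milk carriage is little affected by treatment and not nested in swab carriage. The table above includes cases where the effect is unchanged or stronger.
- *That women without day-6 milk are wrongly scored negative.* Cohort entry in section 6.2 reads "Contributed swabs at day 0 and day 6 (but not necessarily at day 28 or 4 months"), which names swabs and not milk. But Table 5 puts breast milk in its column headed Swab, so day-6 milk may be part of the entry condition. Nowhere does the SAP say that an untested specimen counts as negative, and section 6.4 plans an available case analysis.
- *That the day-0 covariate is invalid because it comes from other specimens.* For E. coli and Klebsiella this would arise only if the any-sample rule also applies at day 0, which section 8.2 does not say. A mismatched pre-treatment covariate costs some precision and does not bias a randomised comparison. For S. aureus, GBS and GAS the only maternal day-0 specimen is the OPS, so the swab site already matches.

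**Conclusion.** The contradiction between sections 3.4 and 8.2 is established from the text alone and needs no assumption: five of the six maternal NPS/OPS endpoints have no analysis as listed. That the composite is a different quantity, unable to show which site changed, also follows from its definition.

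The direction and size of the difference between composite and listed endpoint are not determined by the SAP. The range of pooled odds ratios from 0.42 to 0.71, around a swab odds ratio of 0.51, rests wholly on assumed prevalences and on independence between sites. It shows only that the difference can be material in either direction.

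The primary endpoint, the milk endpoints and S. pneumoniae in NPS are unaffected. The resistance endpoints (items 21 to 25) are listed by bacterium and not by specimen, so pooling does not contradict them.

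**What to change.** In section 8.2, under maternal carriage, add day-6 NPS-only comparisons for E. coli and Klebsiella (items 15 and 17) and OPS-only comparisons for S. aureus, GBS and GAS (items 18 to 20). Analyse each in women with that specimen at day 6, by logistic regression adjusted for the day-0 result from the same site, with the existing 4% rule deciding when Fisher's exact test is used instead.

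Report the any-specimen outcome alongside, labelled as such, in women with all relevant day-6 specimens. This settles how an untested specimen is handled. It should apply whatever the result of the available specimen, since keeping swab-positive women and dropping only swab-negative women who lack milk would inflate prevalence.

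The cost is SAP wording and five more table rows from samples already taken. The downside is five more secondary comparisons, all already listed as endpoints.

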## 6.6 Accounting for differences between countries

(ICH E3; 9.7.1, 11.4.2.4. ICH E9; 3.2)

The regression models used to analyse outcomes in the Primary and Anthropometric cohorts will include country. Hence these analyses will be adjusted for country (in addition to 1-minute Apgar score and birthweight). In the analysis of the Primary cohort, we will do separate analyses in each country using a Wald test to test the treatment x country interaction. This analysis will be considered to be exploratory. No adjustment for country will be made in the analysis of the Carriage cohort because of the smaller size of this cohort.

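### The 4% prevalence cut-off for carriage outcomes is calibrated to all 500 selected dyads and no longer secures 10 events per parameter once about 5% of them are not analysed

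*SAP*

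**What the plan says.** Section 8.2, Maternal carriage, sets the main model: "We will use logistic regression to compare the proportion positive by study arm adjusting for carriage at day 0". It then gives the exception, "If the prevalence of a carriage outcome is <4% then an unadjusted odds ratio will be presented instead of the adjusted OR", with the p-value from Fisher's exact test, and the reason for the threshold: "The cut-off of 4% has been chosen to ensure that logistic regression is not used when there are fewer than 10 events per parameter". The Infant carriage subsection uses the same 4% threshold, adjusting for the mother's day-0 carriage. The subsection on resistant isolates says that its analysis follows that of overall carriage, with everyone tested as the denominator.

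Section 6.6 keeps country out of the model: "No adjustment for country will be made in the analysis of the Carriage cohort because of the smaller size of this cohort".

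On numbers, section 4.1 says that samples "were collected from 500 randomly selected mother-newborn dyads" (or triads). Section 6.2, Carriage cohort, then restricts the analysis set. A dyad must belong to the primary analysis cohort and must have "Contributed swabs at day 0 and day 6 (but not necessarily at day 28 or 4 months"). It must also have "All members of the dyad/triad alive and participating in the study at the time of the" 4-month visit. Section 6.4 adds: "We anticipate some missing data at the 4-month time point because of the interruption due to the COVID-19 pandemic". Within section 8.2, women without day-28 or 4-month data are left out of the main analysis of positivity at any post-treatment time point, and the first version of the breast milk longitudinal analysis uses only women with all three samples. The infant analyses are likewise done on complete data first. Each is repeated on multiply imputed data.

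**The concern.** The SAP gives the threshold a stated property, a minimum of 10 events per parameter. A percentage can deliver a minimum count only for the sample size at which it was set. Here that size appears to be the number selected, while the SAP's own rules make a smaller analysed number foreseeable. No expected analysed number is given and the 4% is not rescaled.

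The threshold decides which estimate and which test are reported for every maternal, infant and resistance outcome in the carriage sub-study. If the analysed number is low enough, an outcome just above 4% goes to adjusted logistic regression although the SAP's own criterion would send it to Fisher's exact test.

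**Working it through.** **Inputs**
- Cut-off: 4%, with logistic regression at or above it (section 8.2).
- Target: at least 10 events per parameter (section 8.2).
- Parameters: 2, study arm and day-0 carriage (section 8.2). Country adds none (section 6.6).
- Number selected: 500 dyads or triads (section 4.1).
- Number analysed: not stated. The values of N below 500 used here are assumptions. The only loss figure in the SAP is the main trial's planning allowance of 8% (section 5); applied to the carriage cohort it gives 500 × 0.92 = 460.

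**Reproducing the SAP's figure.** Events needed = 10 × 2 = 20. Cut-off = 20/500 = 4.0%, an exact match. If the intercept were counted as a third parameter, 20 events would give 20/3 = 6.7 per parameter and the cut-off would have to be 30/500 = 6%. So the SAP evidently used two parameters, N = 500 and both arms combined.

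**Fewest events that pass the rule at smaller N.** Formula: 0.04 × N, rounded up to a whole number; divide by 2 for events per parameter. The cut-off that would restore 20 events is 20/N.

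| N analysed | 0.04 × N | Fewest events passing | Per parameter | Cut-off needed (20/N) |
|---|---|---|---|---|
| 500 | 20.0 | 20 | 10.0 | 4.00% |
| 490 | 19.6 | 20 | 10.0 | 4.08% |
| 476 | 19.04 | 20 | 10.0 | 4.20% |
| 475 | 19.0 | 19 | 9.5 | 4.21% |
| 460 (8% loss, assumed) | 18.4 | 19 | 9.5 | 4.35% |
| 450 (assumed) | 18.0 | 18 | 9.0 | 4.44% |
| 400 (assumed) | 16.0 | 16 | 8.0 | 5.00% |

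The property therefore holds for losses of up to 24 dyads (24/500 = 4.8%) and is gone at 25 (25/500 = 5%).

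**Which outcomes can be misrouted.** Only those that pass 4% with fewer than 20 events. At N = 460 that means exactly 19 events (19/460 = 4.13%; 18/460 = 3.91% already goes to Fisher's test). At N = 450 it means 18 or 19 events, and at N = 400 it means 16 to 19.

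**Where N is likely to fall short.** The cohort criteria in section 6.2 apply to every carriage analysis. The complete-data analyses lose the missing visits as well, so the two losses add up there. Multiple imputation restores missing day-28 and 4-month values within the cohort, but not dyads that the criteria exclude. In infant analyses twins work the other way: with 510 infants (assumed) the rule requires 21 events, or 10.5 per parameter.

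**The case against.** The strongest defence is that the SAP's arithmetic is correct. It is a planning figure that reproduces exactly, and it tolerates a loss of almost 5%. With the only loss figure in the document, 8%, the shortfall is a single event. Ten events per parameter is a rule of thumb, and nothing here shows bias or inflated error at 9 or 8. The SAP gives no carriage prevalences, so no outcome is shown to lie in the narrow band between 4% and 20/N. The maternal day-6 comparison is not cut to complete data. Positivity at any post-treatment time point cannot be rarer than positivity at day 6 in the same women, so it is less likely to sit near 4%. All of this stands, and it limits the size of the point. It does not rescue the claim that the cut-off ensures the minimum, because the document's own exclusions make a loss of 5% or more foreseeable.

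Three stronger readings are tempting and should not be drawn:
- **That the rule works only with all 500 dyads.** Whole-number counts keep it intact down to 476.
- **That many carriage outcomes will be wrongly analysed.** The rule governs many outcomes, but only those in the narrow band can be misrouted, and the document does not show that any are.
- **That the SAP errs by setting no limit near 100% prevalence.** Scarce non-events do strain logistic regression in the same way as scarce events. But the SAP's sentence concerns events only, and no outcome is shown to approach 96%. A limit there would extend the rule, not correct it.

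**Conclusion.** The point holds in a limited form. As a fixed percentage, the cut-off has its stated property only when at least 476 are analysed. The shortfall depends on an analysed number that the SAP does not give: half an event per parameter if 8% loss is assumed, one at N = 450 and two at N = 400. It is most foreseeable in the complete-data analyses and may be partly offset by twins in the infant analyses. The consequence is confined to sparse secondary outcomes of the carriage sub-study, where it affects whether an adjusted or an unadjusted odds ratio is reported. It is worth correcting because the threshold is a pre-specified decision rule with a stated purpose, and a count achieves that purpose at any sample size.

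**What to change.** In section 8.2, replace the 4% rule with a count rule for maternal, infant and resistance outcomes: adjusted logistic regression is used only if the analysed set for that outcome contains at least 20 events, both arms combined; otherwise the unadjusted odds ratio is reported with Fisher's exact test. This also makes explicit that the count is pooled over arms, which the present wording leaves to the reader. It should be settled before unblinding, since it determines which estimate is reported.

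Requiring at least 20 non-events as well is an optional extension.

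The change is one sentence, repeated or cross-referenced in the infant and resistance subsections, and needs no new data. Its downside is that a few low-prevalence outcomes lose covariate adjustment. Where twins bring an infant analysis above 500, the count rule can instead admit an outcome just under 4% to the adjusted model: 20/510 = 3.92%.
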